Materials and methods

Participants

Thirty patients with T1D who had been treated with basal-bolus insulin regimen were recruited at the Mustafa Eraslan and Fevzi Mercan Children's Hospital, Erciyes University in Turkey. There were 14 males and 16 females, with a median age of 16 years (range 16 to 18 years) and a median duration of diabetes 6.0 years (range 2 to 16 years). Median body mass index (BMI) was 20.5 ± 3.01 kg/m² (range 15.6 to 25.0 kg/m²) and glycated haemoglobin (HbA1c) was 7.6 (range 6.0 to 11.2%). The bolus and basal insulin regimen was consisting of lispro (n=4) or aspart (n=26) as fast-acting insulin and insulin glargine (n=23) or detemir (n=7) as long-acting insulin.

Exclusion criteria included: subjects (i) had any restrictive food intake disorders (eg celiac disease or food allergy); (ii) had any diabetes complications (eg neuropathy, nephropathy or retinopathy); (iii) diagnosed for <1 year; (iv) were using corticosteroid or any medication that could effect gastric emptying; (v) did exercise or had hypoglycemia or ketoacidosis within 24 hour before the test meals; (vi) had overweight or obese (BMI z score: $\geq 1SD$ and $\geq 2SD$ respectively); (vii) had not on follicular or peri-ovulatory phases of their menstrual cycles (for females).

Study design

This was a single center, crossover, randomized, controlled study, one standard control meal (SM) and three test meals (HPM: high protein meal using carbohydrate counting method, HPFM-a: high protein-fat meal using carbohydrate counting method and HPFM-b: high protein-fat meal using carbohydrate and fat-protein counting method) were compared on postprandial glucose response. During the first visit at the clinic, all patients and their parents were instructed about the study. The study was approved by the Ethics Committee on Clinical Research Ethics of Erciyes University, Faculty of Medicine (2013/173). A written informed consent was obtained from the patients and their parents.

Dietary intervention

Control and test meals

On four different occasions each interspersed by 1 week, patients consumed in a random order, one standard control meal (SM) and three test meals (HPM, HPFM-a and HPFM-b).

Each meal was given early in the morning at the same time (08.30 h) and prepared in the hospital kitchen. The breakfast meal was chosen as a test meal to eliminate any confounding second-meal effect. Controlled conditions were employed throughout the study and the factors that adversely affects glycemic response has been minimized: All meals were consumed within 20 min; no additional food or drink was allowed in the 4-h postprandial period unless required to treat symptomatic hypoglycemia. Activity was limited to sedentary activities in the research unit (watching DVD). Fast-acting insulin was injected on the same region on arm before the first blood sample collection.

The same amount of carbohydrate (70 g) and fiber (11.5 g) was given to each patient with control and test meals. The energy of SM (543 kcal) was calculated as 25% of subjects' age-adjusted daily energy requirement. HPM and HPHF meals contained same amount of protein (36 g), but differed in fat content (HPM= 17 g, HPHF= 30 g). For SM, HPM, HPFM-a, the insulin doses were calculated according to the carbohydrate content of the meals, for HPFM-b the insulin dose was calculated according to insulin-to-carbohydrate ratio (ICR) and additionally insulin-fat ratio. The composition of standard and test meals and total insulin administration for each meal were given in Table 1.

Table 1. Composition of test meals

Parameters	Unit	SM	HMP	HPFM-a	HPFM-b
Energy	kcal	535	591	702	702
Carbohydrate	g	70	70	70	70
	%	53	49	41	41
Protein	g	24	36	36	36
	%	18	25	21	21
Fat	g	17	17	30	30
	%	29	26	38	38
Fiber	g	11.5	11.5	11.5	11.5
Calculated GI	%	60.4	60.4	60.4	60.4
Total insulin administration (mean±SD)	IU	7.9±1.6	7.9±1.6	7.9±1.6	11.9±1.6

Intervention

Calculation of insulin dosages

For CARB counting meals (SM, HPM, HPFM-a) all patients were subjected to intensive insulin therapy using insulin–carbohydrate ratio for dosing mealtime boluses. Current ICR which was calculated by dividing the total daily insulin dosage into 500 and basal insulin dosages were applied to the current individual therapy of the patient and did not chance

during the control and test meals. Fat and protein was not included in the carbohydrate counting algorithms.

For fat protein counting meal (HPFM-b) ICR and additionally insulin–fat ratio were used for dosing of mealtime boluses. The fat–protein unit (FPU) is defined as 100 calories of fat and protein. HPFM-b meal accounted for 4 FPU (400 kcal from fat and protein).

Assessment of HbA1c and blood glucose concentrations

During the first visit at the clinic, fasting blood samples were collected for HbA1c. HbA1c concentration assessed using turbidimetric inhibition method (ELISA kit), in accordance with the manufacturer's instructions .Subjects arrived to the hospital in a fasting state (after 8 hours night fasting) at 8.00 am and capillary blood glucose values were collected and recorded before (0 min) and every 30 minutes thereafter for 240 minutes (30, 60, 90, 120, 150, 210, and 240 minutes) after control and test meals using glucometer (Accu-Chek; Roche, Mannheim, Germany). Subjects with fasting blood glucose (FBG)> 250 mg/dL or 200-250 mg/dL and urine ketone (+) were excluded and control and/or test meals were repeated in a different day. Test was finalized when hypoglycaemia occurred and repeated in a different day. In case of hypoglycaemia (glucose values below 70 mg/dL, 2 episodes) patients were asked to consume 2 dextrose tablets. No patient had severe hypoglycaemia during the study.

Glycemic response of the meals

Early (0-120 min), late (120-240 min) and whole (0-240 min) glycemic response of standard and test meals were evaluated by area under curve (AUC) calculation.

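### Choosing breakfast cannot by itself remove a second-meal effect: no control of the previous evening's meal is described, which may add within-patient noise but not systematic bias

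*Protocol*

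**What the plan says.** Under Control and test meals (Dietary intervention), the protocol states: "The breakfast meal was chosen as a test meal to eliminate any confounding second-meal effect". The timing is given in the same section: "Each meal was given early in the morning at the same time (08.30 h) and prepared in the hospital kitchen".

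Three controls act before a session starts:

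- The fast, under Assessment of HbA1c and blood glucose concentrations: "Subjects arrived to the hospital in a fasting state (after 8 hours night fasting) at 8.00 am".
- Exclusion criterion (v), under Participants, for patients who "did exercise or had hypoglycemia or ketoacidosis within 24 hour before the test meals".
- The fasting-glucose limit, also in the Assessment section: "Subjects with fasting blood glucose (FBG)> 250 mg/dL or 200-250 mg/dL and urine ketone (+) were excluded". The session was then repeated on another day.

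The listed controlled conditions concern the session itself: "All meals were consumed within 20 min; no additional food or drink was allowed in the 4-h postprandial period", sedentary activity, and a fixed injection region. The design is a four-period crossover: "On four different occasions each interspersed by 1 week, patients consumed in a random order, one standard control meal (SM) and three test meals".

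**The concern.** A second-meal effect is the influence of one meal on the response to the next. For breakfast, the preceding meal is the evening meal or a late snack. Moving the test to breakfast lengthens the gap and rules out an earlier meal that day, but it does not take away the preceding meal. Criterion (v) shows that the day before the session was considered, yet it says nothing about food.

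The point matters more in a crossover. Each patient serves as his or her own control over four mornings, so anything that differs between a patient's four evenings and still acts at 08.30 goes into the error term of every meal contrast. Two of those contrasts rest on modest nutrient differences in Table 1: 36 − 24 = 12 g of protein between HPM and SM, and 30 − 17 = 13 g of fat between HPFM-a and HPM. The trial also studies a late window (120-240 min) and doses for fat and protein in HPFM-b. A study built on those nutrients mattering should say how they were handled in the meal before.

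**Working it through.** The protocol shows no sample-size, standard-deviation or carry-over figure that bears on this point, so there is no figure of its own to reproduce. Three checks follow.

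**1. Length of the gap.** Inputs: 8-hour fast, arrival at 08.00, meal at 08.30.

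- Fast counted to arrival: 08.00 − 8 h = 24.00 for the last food, and 24.00 to 08.30 is 8.5 h.
- Fast counted to the meal: 8.0 h.

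**2. What each pre-session control covers.**

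| Control | What it restricts | Evening meal content or timing? |
|---|---|---|
| 8-hour fast | Latest time of food | Latest time only |
| Criterion (v) | Exercise, hypoglycaemia, ketoacidosis in 24 h | No |
| Fasting-glucose limit | Above 250 mg/dL, or 200-250 mg/dL with ketones | No; acts only on a high fasting value |

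The glucose limit closes one route by which the evening could carry over, but loosely. A ketone-negative patient may start at any value up to 250 mg/dL. The Assessment section puts hypoglycaemia below 70 mg/dL, so the admitted range is up to 250 − 70 = 180 mg/dL wide. That is what the rules allow, not an observed spread.

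**3. What standardising the evening meal could gain (illustration).** Let f be the share of the variance of a paired difference that comes from evening intake and would be removed by holding it constant. The standard deviation of the difference is then multiplied by √(1 − f), and so is the confidence-interval width. Assume n = 30 (Participants), two-sided alpha 0.05, a normal approximation, and a contrast with 80% power before the change. Alpha, power and f are assumptions and are not in the document.

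- Detectable difference before the change: (1.960 + 0.842)/√30 = 0.51 standard deviations of the paired difference.
- Power after the change: Φ(2.802/√(1 − f) − 1.960).
- Equivalent number of unstandardised patients: 30/(1 − f).

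| f | √(1 − f) | Interval shorter by | Power after | Equivalent n |
|---|---|---|---|---|
| 0 | 1.000 | 0% | 80% | 30.0 |
| 5% | 0.975 | 2.5% | 82% | 31.6 |
| 10% | 0.949 | 5% | 84% | 33.3 |
| 20% | 0.894 | 11% | 88% | 37.5 |
| 30% | 0.837 | 16% | 92% | 42.9 |

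The document cannot place f anywhere in this table, and f = 0 is possible.

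**The case against.** The strongest reply is that the protocol speaks of a *confounding* effect, and confounding is largely dealt with. Breakfast removes any same-day meal, and random order breaks any average link between evening intake and test meal. **This stands.** A reader might infer that the comparisons are biased, but the design as described does not support that.

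Second, silence is not evidence of free eating. The protocol says controlled conditions applied throughout, and that patients and parents were instructed at the first visit, without giving the content of that instruction. **This stands too.** One may say only that no control of the evening meal is described, not that evening meals were uncontrolled or in fact varied.

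Third, nothing in the document shows that a meal still acts after 8 hours. The longest response window is 4 hours, about half the gap. **This stands as a limit on the claim:** noise is a possibility and its size is unknown. It does not rescue the absolute wording, since the document offers no evidence that the effect is zero either.

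Fourth, not every contrast rests on a small nutrient difference. HPFM-b and HPFM-a are the same meal with mean insulin of 11.9 against 7.9 IU, which is 4.0/7.9, or about 51%, more. With no AUC difference or standard deviation given, one cannot say that evening variation would hide any contrast. **This also stands.**

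**Conclusion.** The point holds as a minor matter of precision and wording. The described procedures do not deliver elimination of any second-meal effect: a preceding meal may end 8 to 8.5 h before the test meal, and no stated control reaches its content or, beyond a latest hour, its timing. Differences between evenings may add within-patient noise to every contrast. The illustrative gain from removing that noise runs from nothing at f = 0 to intervals 16% shorter at f = 30%, and rests wholly on the assumed f.

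The conclusion does not extend to systematic bias, to a finding that evening intake really was free, or to a claim that the nutrient contrasts would be masked. No figure in the protocol is wrong on this point.

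**What to change.** Ask each patient to repeat, before all four sessions, the usual evening meal eaten before session 1, at about the same time, and to record it in a short diary. The same should apply to any session repeated on another day. Set no rule on overnight snacks or on treatment of hypoglycaemia; those stay as the protocol and usual care have them. In Control and test meals, write *reduce* in place of *eliminate*.

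The cost is one instruction and a brief diary entry per session, with no added visit or procedure. The downside is a small burden on patients and imperfect adherence, which would shrink any gain.

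The protocol is written in the past tense. If the sessions are over, what remains is the change of word and a sentence saying whether the previous evening's meal was standardised or recorded.

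### Is it an error that the AUC outcome names neither total nor incremental area and is not adjusted for starting glucose?

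*Protocol*

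**What the plan says.** The outcome appears only in the Protocol's last section, Glycemic response of the meals: for 0-120, 120-240 and 0-240 minutes, "glycemic response of standard and test meals were evaluated by area under curve (AUC) calculation". No baseline is named and no statistical model is given anywhere in the document.

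Starting glucose does appear under Assessment of HbA1c and blood glucose concentrations. At each session, "capillary blood glucose values were collected and recorded before (0 min") and then through 240 minutes. Two rules limit where a session can start or how it can continue: "Subjects with fasting blood glucose (FBG)> 250 mg/dL or 200-250 mg/dL and urine ketone (+) were excluded", with the meal repeated on another day, and "Test was finalized when hypoglycaemia occurred and repeated in a different day". The threshold for the second is given as "In case of hypoglycaemia (glucose values below 70 mg/dL, 2 episodes").

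The design section states that "patients consumed in a random order, one standard control meal (SM) and three test meals", one week apart. Under Control and test meals, the mealtime dose follows meal content, with no stated term for starting glucose, and the injection comes before the first blood sample. Table 1 gives a mean dose of 7.9 IU for three meals and 11.9 IU for HPFM-b, the meal dosed by carbohydrate plus fat-protein counting.

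**The concern.** A total area carries the starting level through the whole window. If one session starts at 70 mg/dL and another at 250, and the difference persists, the 0-240 minute area differs by 180 × 240 = 43,200 mg/dL × min with no meal effect at all. An incremental area subtracts that amount. The text does not say which is meant, the permitted starting range is wide, and only 30 patients are studied. A reader may therefore fear that chance differences in starting glucose are taken for meal effects, or that precision is lost when a recorded covariate goes unused. HbA1c also varies widely between patients ("glycated haemoglobin (HbA1c) was 7.6 (range 6.0 to 11.2"%), which suggests that starting levels do too.

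**Working it through.** **No figure to reproduce.** The Protocol gives no SD, correlation, effect size, significance level or power. Everything below on precision rests on assumed values.

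**Does the unadjusted area mislead?** Every patient eats every meal, so stable differences between patients, including those reflected in HbA1c, cancel in within-patient contrasts. What remains is session-to-session variation, with SD s. For two meals in 30 patients, the SE of the chance difference in starting glucose is s × √(2/30) = 0.258 s.

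- Assumed s of 20 to 50 mg/dL: SE 5.2 to 12.9 mg/dL, a 95% range of about ±10 to ±25 mg/dL. Times 240, this is about ±2,400 to ±6,100 mg/dL × min if fully carried through.
- Wide case, starting values uniform over 70 to 250: s = 180/√12 = 52.0, SE 13.4 mg/dL.

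This variation is already inside the residual error of the unadjusted contrast, so its standard error allows for it. A simulation of 30 patients × 4 meals confirms this (patient fixed effects, starting SD 40 mg/dL, within-patient correlations of 0.22 to 0.85, 1,500 runs each). Type I error was 4.9 to 5.9% for total area and 4.8 to 5.9% across total, incremental and adjusted areas. The Monte Carlo SE at 5% is √(0.05 × 0.95/1500) = 0.56 points, so all are compatible with 5%.

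**What would adjustment buy?** Let ρ be the within-patient correlation of starting glucose with AUC. With patient, meal and period in the model (an assumed model), residual df = 120 - 1 - 29 - 3 - 3 = 84. The expected variance of the adjusted contrast relative to the unadjusted one is (1 - ρ²)(1 + 1/82). Plain subtraction of the starting value gives 1 + k² - 2ρk, where k is the SD of starting glucose over the SD of mean glucose; k = 1 is shown.

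| ρ (assumed) | 1 - ρ² | Adjusted, net | Effective N | Subtracted (k = 1) |
|---|---|---|---|---|
| 0 | 1.00 | 1.012 | 29.6 | 2.0 |
| 0.2 | 0.96 | 0.972 | 30.9 | 1.6 |
| 0.5 | 0.75 | 0.759 | 39.5 | 1.0 |
| 0.7 | 0.51 | 0.516 | 58.1 | 0.6 |

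Adjustment breaks even at ρ² = 1/83, that is ρ ≈ 0.11. The result runs from a 1% loss to a 48% gain, and nothing in the Protocol says where in that range the trial lies. Choosing the incremental area could double the variance.

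**Is the covariate clean?** The only starting value documented for every session is the 0-minute sample. By the Protocol's own sequence it follows the injection, after an unstated interval, and the mean dose differs by 11.9 - 7.9 = 4.0 IU between HPFM-b and the other meals. The glucose used for the repeat rule might be a separate, earlier reading, but the document does not establish that. For contrasts with HPFM-b the covariate may therefore not be strictly pre-treatment.

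**The case for a change.** The strongest counter-argument concerns the definition of the outcome. Total and incremental area are different quantities. In the same simulation they disagreed on significance in 8 to 10% of trials with no effect and in 29 to 36% of trials with a true effect of 25 mg/dL. Reporting whichever is significant would raise type I error from 5% to about 9 to 10% per contrast. That arithmetic stands, and the type should be fixed somewhere. But the harm requires the choice to be open in the analysis plan as well, which cannot be seen. Taken at face value, an area under the curve with no baseline named is the total area, though the words do not exclude the other reading.

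A second argument is that at ρ of 0.5 or more the gain is too large to ignore. This is true if ρ is that large, but it argues for a better analysis and does not show the present one to be wrong. The text reports completed conduct, so an adjustment not already planned would be post hoc and would add a further set of results in three windows.

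The wide starting range counts for less than it seems. Sessions follow an overnight fast, arrival and meal times are fixed, and the Protocol excludes patients who "did exercise or had hypoglycemia or ketoacidosis within 24 hour before the test meals". These conditions limit the spread without removing it.

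One reservation applies to the defence itself. Random order does not protect against repeats triggered after the meal has been given, which could depend on the meal. If the count of 2 is the number of hypoglycaemia episodes in the study, that is 2 of 120 sessions (1.7%), too few to change the conclusion.

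**Conclusion.** The concern does not hold. The text is silent on area type and on starting glucose, but it states nothing wrong, contradicts nothing and commits to no model that ignores the starting value. Both matters are commonly settled in the analysis plan. The unadjusted comparison is valid under random meal order, with simulated type I error close to 5%. The possible precision gain, from +1% to -48% of contrast variance for ρ between 0 and 0.7, rests wholly on an assumed correlation. The suggested covariate has its own difficulty, because it is sampled after injections of unequal mean dose. The conclusion assumes that order was randomised as stated and that repeated sessions were few. It does not claim that starting glucose is unimportant, only that the Protocol's silence on it is not a defect.
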